# Safety Telephone Calls (Day 14, Day 42, Day 70)

At times during the study, the site personnel will call the subject and/or their parent/caregiver to see if they are adjusting well and whether they are having any difficulties on the medication. The subject will be

contacted by the study team by telephone at day 14, day 42, and day 70after the start of study drug and the following will be discussed:

- 1. Review of any current adverse events and/or adverse events of special interest that the subject has experienced.
- 2. Review of all medicines the subject is currently taking.

# Virtual Visits

Virtual visits will be conducted in between scheduled clinic visits in the extension portion of the study to assess patient wellbeing. After a year of follow up in the extension period, virtual visits will be conducted as deemed necessary by the LPI. Partners enterprise platforms (Patient Gateway) will be used to conduct these visits.

# Post-Dosing Telephone Follow-Up Visit (14 Days After Last Dose of ZX008)

After the subject has completed the study, or discontinues from the study early, the site personnel will call the subject and/or their parent/caregiver at the Post-Dosing Telephone Follow-Up Visit (14 days after the day of discontinuation):

- Review the subject's current epilepsy status since the previous visit including: the amount of seizures they had, the types of seizures they experience, and the duration of each of their seizure types.
- Review about how the subject is feeling and what medicines they have taken.
- Review of any current adverse events and/or adverse events of special interest experienced by them, after the previous visit.
- The subject's seizure diary will be reviewed with them or their parent/caregiver.

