# **V. STUDY PROCEDURES**

The investigational drug to be used in this study is fenfluramine hydrochloride (ZX008) manufactured by Zogenix, Inc..

ZX008 will be supplied as an oral solution in a concentration of 2.5 mg/mL. The subjects will be treated on an outpatient basis and will not require hospital admission. ZX008 will be administered on a twice daily basis.

The study will initially consist of a 4 week baseline period, during which handwaving associated with absence seizures and/or generalized tonic-clonic seizures will be recorded in a seizure diary on a daily basis. Subjects will meet enrollment criteria if they have an average of 6 generalized tonic-clonic and/or handwaving associated absence seizure per week.

If enrollment criteria is met, the subject will enter a titration period. The starting dose will be 0.2 mg/kg/day for the first 14 days. The dose will be increased every 2 weeks as tolerated by 0.2 mg/kg/day, to a maximum dose of 0.8 mg/kg/day, or a total maximum dose of 30 mg/day. The subject will remain on 0.8 mg/kg/day, 30 mg/day, or maximum tolerated dose for a 6 week maintenance period.

Site personnel will call the subject and/or their parent/caregiver every 11-14 days during the titration period before their next scheduled dose increase.

There will be 5 study visits within a 6 month period. After Visit 5, visits will occur every 6 months for an assessment in the clinic for subjects who respond to treatment with at least a 30% reduction in seizure frequency.

Seizure frequency will be tracked with the use of a daily seizure log. In the event that seizure frequency is markedly reduced compared to baseline after starting the study drug the LPI will discuss with the subject and/or their caregiver about adjusting the dose of concomitant seizure medications. If seizure frequency is markedly increased compared to baseline after discontinuing other medications which were taken as standard of care the LPI may decide to adjust dose of other seizure medications or reintroduce the medications that were taken as

IND Visit Schedule					
Visit Number	Visit Type	Time Point			
1	Baseline	Day -28			
2	Titration	Day 1 (+14 days)			
3	Titration and/or	28 days from Visit 2			
	Maintenance	(±7 days)			
4	Maintenance	56 days from Visit 2			
		(±14 days)			
5	Maintenance	84 days from Visit 2			
		(±14 days)			
Continuous	Maintenance	Each 6 Months			
		following Visit 5			
		(±14 days)			

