#### At Visit 1, 2, 3, 4, 5, (Day -28, Day 1, Day 28, Day 56, Day 84) and All Sequential Visits

For the period during which COVID-19 contingency plans are in place at Partners/MGH, all study visits, including the Screening Visit, will be conducted as telemedicine appointments through a PHS IS-approved Zoom software. A weblink will be provided to subjects ahead of each appointment.

For study visits conducted as telemedicine appointments, required study procedures will be performed at sites local to the subject. We will provide each subject with location and scheduling information for their respective local site. The required study procedures that will be performed locally are:

- Echocardiograms (Visits 1, 5 and Extension Visits 1 and 2)
- Labs (CBC, CMP, AED) (as required by Principal Investigator)

Echocardiograms, and labs (CBC, CMP, AED) conducted locally will be sent to the Principal Investigator to ensure patient safety, and, in the case of ECHOs returning positive results, will be sent to a central reader, BioMedical Systems, Inc. (BMS).

These visits will take about 2 hours. During these visits, the following will be conducted:

- All the study eligibility criteria will be reviewed to confirm that the subject is still eligible.
- The subjects past and current medical, neurological, and epilepsy history will be reviewed at Visit 1 only.
- The study doctor will review the subject's current epilepsy status from the previous visit including: the amount of seizures they had, the types of seizures they experienced, and the duration of each of their seizure types.
- The subject will be asked about their health and the medicines that they have taken or are currently taking.
- Perform a physical and neurological exam. These exams are a series of simple questions and tests that provide very important information about the subject's systems. During the neurological exam, the treatment doctor will ask the subject to stand straight and walk, see how well the subject can move during the visit, and talk to the subject to see how they are doing. The treatment doctor will also look at the subject's eyes and see how their face, arms, and legs feel when touched.
- Vital signs including: blood pressure, heart rate, respiratory rate, along with height, and weight will be measured.

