- At Visit 1, 5 and all subsequent visits a Doppler echocardiogram (ECHO) will be done using ultrasound waves for examination of the heart. This will be performed at a cardiology clinic/office which may be separate from the study doctor's office, and may be done on a different day. The subject might receive a sedative medication for this procedure if they cannot be still for the test. In this test, the subject will be lying on a bed and a person will move a wand on their chest. This transmits information to a monitor to tell how well the subject's heart beats and moves inside their chest. It may also indicate if the subject has an increase in blood pressure in the arteries in their lungs. ECHOs will be completed locally and, if positive results are returned, it will be sent to a central reader, BioMedical Systems, Inc. (BMS) to ensure patient safety.
- At Visit 2, 5, and all subsequent visits, the subject and/or the subject's parent/caregiver will be asked to complete the following:
  - The Columbia-Suicide Severity Rating Scale (C-SSRS) questionnaire to see if they have ever thought about harming or killing themselves or behaved like they wanted to harm or kill themselves, if applicable.
  - Premonitory Urge Scale
  - If the subject is between 7-18 years he/she will be asked to complete:
    - the Beck Self Report Inventory to assess selfconcept, depression, anxiety, anger and disruptive behaviors
    - Children's Florida Obsessive-Compulsive Inventory

- Children's Yale-Brown Obsessive-Compulsive symptoms
- If the subject's age is 18 years or older he/she will be asked to complete:
  - Beck depression inventory.
  - Beck Anxiety inventory
  - Yale-Brown Obsessive-Compulsive symptoms
- The subject's caregiver/parent will be asked to complete questionnaires to measure the subject's health as it relates to quality of life, and how their condition affects their dayto-day activities and health. The questionnaires that will be given include:
  - Behavioral Rating Inventory of Executive Function (BRIEF) – to assess executive function
  - Quality of Life in Childhood Epilepsy Questionnaire (QOLCE) – to assess mood, social relationships, behaviors)
  - Attention Deficit Hyperactivity Disorder (ADHD) checklist – to assess for hyperactivity and inattention
- At Visit 2, Visit 5, and Visit 7, Neuropsychological testing will be done to assess cognitive function using the following tests (only for patients 1-10):

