# Cardiac Follow-up (3 Months After Last Dose of ZX008): to examine the heart

If the subject has taken study medication for longer than 14 days and then leaves the study, or if the subject completes the study, the study doctor will perform the following tests and procedures after 3 months of study treatment discontinuation. If a problem with the subject's heart is detected, these procedures might be repeated after another 3 months:

- The study doctor will examine the subject (physical examination).
- A Doppler ECHO will be done using sound waves for examination of the heart. The subject may receive a sedative medication for this procedure if they cannot be still for the test.
- Review of any side effects related to heart safety experienced by the subject after the previous visit.

If the subject is found to have positive findings on ECHO and/or physical examination at the 3-month post dose follow-up the subject will have repeat examinations at 6 months post-dose and then every 3 months until the finding is resolved or stable and unlikely to change, with reports submitted to the ZX008 safety database.

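### Subjects who stop ZX008 before Visit 5 have no ECHO, C-SSRS or quality-of-life assessment at or near the last dose

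*Protocol*

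**What the plan says.** **ECHO schedule.** Section V, in the visit procedures, states: "At Visit 1, 5 and all subsequent visits a Doppler echocardiogram (ECHO) will be done". The list of locally performed procedures for telemedicine visits has the same gap: "Echocardiograms (Visits 1, 5 and Extension Visits 1 and 2". Neither places an ECHO at Visits 2, 3 or 4. The IND Visit Schedule puts Visit 5 at "84 days from Visit 2", with a window of ±14 days.

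**Questionnaires.** The C-SSRS, the mood and obsessive-compulsive scales and the caregiver quality-of-life forms start from: "At Visit 2, 5, and all subsequent visits, the subject". None is due at Visits 3 or 4.

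**After early stopping.** Under Post-Dosing Telephone Follow-Up Visit: "After the subject has completed the study, or discontinues from the study early, the site personnel will call the subject". The call takes place 14 days after discontinuation and reviews seizures, general health and medicines, adverse events and the diary. Under Cardiac Follow-up the condition is "If the subject has taken study medication for longer than 14 days and then leaves the study" (completers are also included). These subjects have a physical examination and Doppler ECHO 3 months after stopping. A positive finding at that point leads to "repeat examinations at 6 months post-dose and then every 3 months until the finding is resolved" or is stable.

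**Reporting.** Section IX requires that ECHO findings consistent with valvulopathy or pulmonary hypertension be notified to the manufacturer.

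**The concern.** Section VII (Thickening of Heart Valves) gives early detection as the purpose of the ECHOs. It also says that valves recovered in some patients after the drug was stopped. The next subsection says that an abnormal ECHO need not come with symptoms. The In Human Trials subsection lists mild, clinically insignificant valve thickening among events seen in Dravet patients at up to 30 mg/day, which is the maximum dose here. An ECHO done only 3 months off drug can therefore miss a silent change that arose on drug and has since regressed. That change would not reach the notification in Section IX. If the 3-month ECHO is abnormal, there is no end-of-drug reading to show whether the valve is improving or worsening.

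The second loss is to the questionnaires. Section II makes quality of life a secondary objective and describes anxiety and depression as frequent in this population. Section IX lists worsening seizures, adverse events and noncompliance among the reasons for withdrawal, so those without a second questionnaire may be subjects who did badly. With at most 20 subjects (Section III), each early leaver is at least 1/20 = 5% of the sample.

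**Working it through.** The protocol states no figure to reproduce. The check is timeline and dose arithmetic.

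**Inputs**
- Visit 5 window: 84 ±14 days from Visit 2, so day 70 to day 98 (IND Visit Schedule).
- Visit 1 ECHO: 28 days before Visit 2, or 28 + 14 = 42 days if Visit 2 uses its +14-day window.
- Post-drug ECHO: 3 months after the last dose, for those dosed for more than 14 days (Cardiac Follow-up). I take 3 months as 91 days; 90 or 92 shifts each result by one day.
- Titration: "The dose will be increased every 2 weeks as tolerated by 0.2 mg/kg/day", starting at 0.2 mg/kg/day, to a maximum of 0.8 mg/kg/day or 30 mg/day.

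**Who is affected**
- Earliest last dose: day 15, the first beyond 14 days of dosing.
- Latest last dose: the day before the subject's own Visit 5, at most 98 − 1 = day 97.

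**First post-baseline ECHO = last dose + 91 days**
- Stop on day 15: 15 + 91 = day 106.
- Stop on day 97: 97 + 91 = day 188.
- Completers: day 70 to 98, on drug.

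**Interval from the baseline ECHO**
- Early leaver: 28 + 106 = 134 days to 42 + 188 = 230 days.
- Permitted interval to Visit 5: 28 + 70 = 98 days to 42 + 98 = 140 days.
- The ranges overlap at 134–140 days. The main loss is that the ECHO is taken off drug, more than that it is late.

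**Exposure at stopping** (fastest titration, weight at or below 30/0.8 = 37.5 kg, so that the 30 mg cap does not bind)

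| Last dose | Cumulative dose (mg/kg) | Share of day 84 |
|---|---|---|
| Day 15 | 14×0.2 + 1×0.4 = 3.2 | 6% |
| Day 42 | 14×(0.2+0.4+0.6) = 16.8 | 33% |
| Day 69 | 16.8 + 27×0.8 = 38.4 | 76% |
| Day 84 | 16.8 + 42×0.8 = 50.4 | 100% |

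An end-of-drug ECHO is therefore most informative for stops from day 43 onward, when the target dose has been reached, and least informative just after day 14.

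**Questionnaires.** They are collected at Visit 2 and next at day 70 to 98. The 14-day call does not list them. A subject who stops in between has none after Visit 2, whatever the length of dosing.

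**What the 3-month ECHO does and does not catch**
- Persistent change: found.
- Change with symptoms: Section VII tells the subject to contact the site, so it may be found sooner.
- Symptom-free change that regresses within 3 months: not recorded and not notified.

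**The case against.** A reader might infer that early leavers are not followed at all, or that valve damage in them would generally be missed. The protocol does not support either reading. It expressly gives them a call at 14 days and, above a stated exposure threshold, an examination and ECHO at 3 months. Subjects withdrawn for an adverse event are followed until it resolves (Section IX), and physical examinations are listed at Visits 3 and 4. The gap is one of timing.

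The ECHO part also rests on a long chain: a stop before Visit 5, a valve change within at most 97 days of dosing, no symptoms, and regression within about 91 days. Section VII says these problems usually develop slowly. Its statement about recovery concerns adults treated for obesity and gives no time course. The subject has already stopped, so no continuation decision depends on the result. A change that has resolved by 3 months is also one the protocol would regard as closed. All of this stands, and it limits the weight of the point.

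A further objection is that an added ECHO alone would not lead to closer follow-up, because the repeat examinations depend on a positive finding at 3 months. That is correct, and that trigger has to be amended as well. It is also fair that an ECHO soon after day 14 yields little, that sedation carries risk, and that the questionnaires are a burden.

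None of these safeguards requires an ECHO near the last dose or any questionnaire after Visit 2. An investigator may order an ECHO on clinical judgement, but the protocol does not ask for one.

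**Conclusion.** The point holds as a minor, cheap improvement. Subjects who stop between day 15 and their own Visit 5 have no scheduled on-drug ECHO, and their first post-baseline ECHO comes about 91 days off drug (about day 106 to 188). All who stop before Visit 5 lack the C-SSRS and quality-of-life forms after Visit 2.

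The safety loss is confined to symptom-free changes that regress within 3 months and to the missing comparison for an abnormal 3-month ECHO. The number of such cases is probably small. It cannot be computed, because the protocol gives no dropout rate, no onset or regression times, and enrols at most 20 subjects. The questionnaire loss is more certain, since it applies to every early leaver.

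This rests on two assumptions: 3 months is about 91 days, and a subject who stops the drug also leaves the visit schedule, since the protocol describes no off-drug attendance up to Visit 5. It would go too far to call this an error or contradiction in the protocol, or to say that these subjects' treatment is compromised.

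**What to change.** Add to Post-Dosing Telephone Follow-Up Visit:

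> A subject who stops ZX008 before Visit 5 will complete the C-SSRS by telephone or video and the Visit 5 caregiver quality-of-life questionnaires by mail, at or soon after the last dose and no later than the 14-day call. If dosed for more than 14 days, the subject will also have the Visit 5 ECHO brought forward to within about 7 days of the last dose, done locally, where feasible without sedation or where the investigator judges sedation justified.

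Amend Cardiac Follow-up so that a positive ECHO at early termination also triggers the repeat examinations. Keep the 14-day call and the 3-month ECHO.

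The first post-baseline ECHO then falls about 0 to 7 days off drug instead of about 91.

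**Cost.** Small. The ECHO is already planned for every subject and done locally. Mailing of questionnaires is already used for virtual visits, though a stand-alone mailing would be new. The downsides are short-notice scheduling, some refusals, occasional sedation (Section VII lists breathing difficulty and a fall in blood pressure among its risks), questionnaire burden, and low ECHO yield for stops soon after day 14.

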# Cardiac Follow-up (3 Months After Last Dose of ZX008): to examine the heart

If the subject has taken study medication for longer than 14 days and then leaves the study, or if the subject completes the study, the study doctor will perform the following tests and procedures after 3 months of study treatment discontinuation. If a problem with the subject's heart is detected, these procedures might be repeated after another 3 months:

- The study doctor will examine the subject (physical examination).
- A Doppler ECHO will be done using sound waves for examination of the heart. The subject may receive a sedative medication for this procedure if they cannot be still for the test.
- Review of any side effects related to heart safety experienced by the subject after the previous visit.

If the subject is found to have positive findings on ECHO and/or physical examination at the 3-month post dose follow-up the subject will have repeat examinations at 6 months post-dose and then every 3 months until the finding is resolved or stable and unlikely to change, with reports submitted to the ZX008 safety database.

# Shipment of ZX008 study drug

If Study Visit 2 is conducted as a telemedicine appointment, we will ship a supply of ZX008 to the subject's home via FedEx to arrive on the day of the scheduled Study Visit 2. If it arrives prior to this visit, or if the visit is re-scheduled for any reason, the subject will be advised not to administer any study drug prior to the study visit and to store it in a cool, dry place at room temperature.

Shipments of ZX008 will be sent to subject's homes via FedEx as they require new supply. Study staff will review the schedule of these shipments with the subject as they may vary for each subject.

# VI. BIOSTATISTICAL ANALYSIS

The data variables to be collected from each subject will include:

- The number and type of seizures occurring per day
- The duration of the seizures
- Complete blood count with differential (CBC with diff), a complete metabolic panel, and current levels of anticonvulsant medication levels
- EEG patterns
- Quality of life assessments

# VII. RISKS AND DISCOMFORTS

#### **Risks of Taking ZX008**

Any research study has risks, which may include things that could make the subject sick, make the subject feel uncomfortable, or harm them. The subject might experience side effects related to the treatment drug while participating in the treatment. The subject will be watched carefully for any side effects; however, the study team does not know all the effects that ZX008 may have on the subject. The study team may give the subject medicines to help reduce side effects. These side effects may be mild or serious. In some cases, these side effects might be long lasting, or permanent, and may even be life threatening.

# Allergic Reaction:

Any drug has a possible risk for an allergic reaction. If the subject has any symptoms that could be an allergic reaction such as feeling faint, having skin swelling, or having difficulty breathing, or experience any worrying health issue, they should seek immediate local medical assistance and then contact the study site.

#### Thickening of Heart Valves; Pulmonary Hypertension:

When the active ingredient in ZX008, fenfluramine, was on the market for the treatment of obesity in adults who were overweight from the 1970s through the 1990s, some adults developed thickening of heart valves and pulmonary hypertension (high pressure in blood vessels in the lung that makes it difficult to breathe normally). After stopping the medication, some patients' heart valves returned to normal, some remained stable but abnormal, and some had surgery to correct the condition. Generally, if these problems do occur, they develop slowly over time. The subject will be administered ECHOs during the study to very carefully watch for early signs that the subject's heart valves are thickening and to look for early signs of pulmonary hypertension. If there are heart valve changes, the subject will re-review the risk and potential benefit of the study medication with the study doctor and discuss further options. The subject may withdraw at this or any other time. If the subject experiences any chest pain, persistent cough, shortness of breath, wheezing, extreme fatigue, or dizziness, they should contact the study staff immediately to discuss whether they should have a clinic visit or other tests.

#### If a Subject Has a Positive Finding on Their Echocardiogram:

A positive finding on one of the echocardiograms may indicate that one or more of the subject's heart's valves are not functioning normally. This detected abnormality may not be associated with any physical symptoms. There are four valves in the heart: the aortic, mitral, tricuspid, and pulmonary. If one or more of these valves are not working properly and the subject continues in this study, they may be at an increased risk. We cannot know for certain whether a positive finding is the result of ZX008 and we do not know for certain whether the condition will worsen with continued use of ZX008. Some adults who have taken the same medication components in ZX008 and developed heart abnormalities have remained stable for years, while some adults who have taken the medication for obesity (excess overweight) developed heart problems that interfered with daily activities, and a small number have needed surgery or a procedure to improve heart function.

All ECHOs will be evaluated by a central reader from BioMedical Systems, Inc. (BMS). The primary investigator and local cardiologist will receive notification in the event of any ECHO findings consistent with pulmonary hypertension or valvulopathy on any of the four valves (aortic, mitral, pulmonary, tricuspid) with grades of normal, trace, mild, moderate, or severe. If the ECHO result has progressed in severity since the last reading, then new oversight measures will be enacted as described below in Levels 1-3. Table 1 describes the severity of ECHO findings with the level of increasing oversight if the subject is to remain in the study.

